## 1.2 SCHEMA

\* Eligibility monitoring with mobile cardiac telemetry provided by Preventice will only serve as an option for potential patients that do not have any clinical ePatch monitoring completed in the past 6 months. Potential patients that have ePatch monitoring results with no change in medication since then, do not have to undergo mobile cardiac telemetry during Eligibility visit. \*\* Activities are to be repeated for control subjects only who choose to crossover to experimental group prior the second procedure. \*\*\*Second procedure is to be done within two weeks of the Week 3 Visit for crossover patients, if not, patient must complete another pre-op visit two weeks before the procedure. Pre-op visit will entail Labs (CBC, BMP), INR if patient is taking Coumadin, 12 Lead EKG and pre-op instructions.

All patients will have baseline cardiac rhythm monitoring using standard ECG patch electrodes. Cardiac rhythm monitoring will be done with clinically available 7-day non-invasive Mobile Cardiac Telemetry.

Among them, the 7-day non-invasive Mobile Cardiac Telemetry provided by Preventice will be performed during the two weeks of ScNS to ensure patient safety. The Bittium Faros monitor, a non-invasive patch electrode, will be applied at similar time points as Preventice Mobile Cardiac Telemetry device to monitor skin sympathetic nerve activity. Mobile cardiac telemetry will also be performed for a week after the end of stimulation and for a week at 3 months after surgery. An Apple watch will be used to detect AF episodes, if any, until the completion of the 3 Month Visit 7-day Mobile Cardiac Telemetry.

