# 5 STUDY POPULATION

## 5.1 INCLUSION CRITERIA

In order to be eligible to participate in this study, an individual must meet all of the following criteria:

- 18 to 75 years of age
- Symptomatic paroxysmal AF unresponsive to conventional therapy.
  - Symptomatic paroxysmal AF is defined by paroxysmal AF with patient-reported perception of one or more of the following symptoms: palpitations, dizziness/presyncope, syncope, dyspnea, chest pain, malaise, and fatigue and activity intolerance.
  - There is at least one ECG-documented AF episode.
  - Unresponsive to conventional therapy is defined by not responding to at least 1 antiarrhythmic drug (class I, class III, or atrioventricular nodal blocker).

- The left atrial size <50 mm by transthoracic echocardiography documented by eligibility visit
- Documented atrial fibrillation as defined as atrial fibrillation >30 seconds in duration with an atrial fibrillation burden determined by a minimum of 7 days of continuous ePatch monitoring within 6 months before surgery.

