## 5.2 EXCLUSION CRITERIA

An individual who meets any of the following criteria will be excluded from participation in this study:

- Patients without AF episodes during monitoring period will be excluded from the study and count as screen failure
- Left ventricular ejection fraction <40%
- Heart failure with functional classes III or IV
- Recurrent vasovagal syncope
- Valvular AF (severe mitral regurgitation, mitral stenosis)
- Congenital heart diseases
- Wolff Parkinson-White Syndrome
- Stroke within the past 6 months
- Any history of myocardial infarction
- Malignancies with a life expectancy of < 1 year
- A history of ablation procedures to treat left atrial tachyarrhythmias or other serious comorbidity
- Any history of sustained ventricular tachycardia (VT) defined by (1) > 30 s in duration or (2) < 30 s in duration, but is associated with hemodynamic consequences such as hypotension and syncope.
- Patients with a vagal nerve stimulator
- Active thyrotoxicosis
- Sick sinus syndrome with symptomatic bradycardia
- Heart rate < 50 beats per minute in sinus rhythm on 12-lead ECG
- Systolic blood pressure < 90 mm Hg
- Any experimental medication concomitantly or within 4 weeks of participation in the study
- Subjects with cardiac implantable electronic device (CIED) such as pacemakers and implantable cardioverter-defibrillators (ICDs)
- Pre-existing neuromodulation devices, such as vagal nerve stimulators, spinal cord stimulators and sacral nerve stimulators
- People with a history of allergy to ECG electrodes, adhesive tape, or nylon
- Pregnant women

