## 9 STATISTICAL CONSIDERATIONS

### 9.1 STATISTICAL HYPOTHESES

*State the formal and testable null and alternative hypotheses for primary and key secondary endpoints, specifying the type of comparison (e.g., superiority, equivalence or non-inferiority, dose response) and time period for which each endpoint will be analyzed.*

- Primary Efficacy Endpoint(s):

The average AF burden.

- Secondary Efficacy Endpoint(s):

- 1) Time-dependent reduction of AF burden
- 2) Ventricular rate during AF
- 3) Average SKNA
- 4) Quality of life
- 5) Reduction of AF burden after cross over from control to experimental group

**Our primary research hypothesis is that** chronic subcutaneous nerve stimulation can control AF in patients with severe symptomatic AF unresponsive to conventional therapies.

The primary endpoint is the average of AF burden at the end of the first week. Patients who do not experience AF during the first week will have a value of 0 as AF burden. The average of AF burden at the end of the first week will be calculated per patient as the proportion of time spent in AF during the first week divided by the number of days a patient is under observation during the first week.

We will test the null hypothesis of no difference in the average AF burden between the treatment groups versus the alternative hypothesis that the average AF burden is lower in the intervention group than the sham group.

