**The following pairs of secondary null and alternative hypotheses will be tested:**

- 1) that the trajectories of reduction of AF burden by time between treatment and control groups are the same versus that the trajectories are different;
- 2) that reduction of AF burden in treatment group does not depend on time versus that the reduction of AF burden is dependent on time;
- 3) that effects of ScNS and sham stimulations on ventricular rate control during AF are the same for the treatment and the control groups versus that the effects are different between the two groups;
- 4) that reduction of SKNA is the same between the treatment and the control groups versus that the reduction of SKNA is different between the two groups;
- 5) that improvement of quality of life is the same between the treatment and the control groups versus that the improvements of QoL is different between the two groups.
- 6) There is a reduction of AF burden after crossing over from control to experimental group

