### 9.2 SAMPLE SIZE DETERMINATION

The AF burden is determined by the amount of time spent in AF detected by Mobile Cardiac Telemetry patch. A recent study analyzed the results of ambulatory single-lead ECG patch sensor monitoring for 11.4 days on average in 7934 men and 5359 women with paroxysmal AF. During the monitoring period, there were a total of 1,041,504 paroxysmal AF episodes. The median daily rate of paroxysmal AF was 1.21 episodes per day (interquartile range [IQR] 0.31-4.99), and the median maximum duration per individual was 7.5 hours (IQR 2.4-18.6 hours). The median burden of AF (% of time in AF relative to entire period of monitoring) was 8.9% (IQR 3.4%-25.2%). Assuming that we implant the lead and randomize patients into experimental group (stimulation) and control group (no-stimulation), we expect to see the same average AF burden among our patients. In our previous study in canine models, subcutaneous nerve stimulation reduced atrial arrhythmia burden per 48 hours from  $211.0 \pm 204.8$  s to  $134.8 \pm 165.2$  s ( $\Delta = -76.3 \pm 44.8$  s) versus a reduction of  $-5 \pm 9.5$  seconds in the sham group. Assuming the same standard deviation of the change of AF burden from baseline in the two randomized groups as 44.8 and accounting for the patient retention rate of 70%, we need 15 per arm (total 30 patients) for 80% power at 2-sided alpha 0.025 to detect an effect size of 1.59 at the end of one week between Group A (experimental) and Group B (control) using the Wilcoxon rank sum test. If the treatment suppresses AF by 75% while the sham does not suppress AF at the end of one week, we have 86% power to detect this difference at 2-sided alpha 0.025 using Fisher's exact test. We have budgeted for 32 patients to ensure that we have sufficient funds to complete the study.

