#### 9.4.2 ANALYSIS OF THE PRIMARY EFFICACY ENDPOINT(S)

The primary endpoint is the average of AF burden at the end of the first week.

We will use Mobile Cardiac Telemetry to determine AF burden before surgery (eligibility visit), for two weeks during ScNS, 3 weeks following surgery and 3 months following surgery.

The average of AF burden at the end of the first week will be calculated per patient as the time spent in AF during the first week divided by the total time a patient is under observation during the first week. Change of the average AF burden from the baseline will be computed for each patient. The change in the average AF burden will be compared between group A (experimental) and group B (control) using the Wilcoxon rank sum test at a two-sided significance level of 0.025.

*The following secondary analyses of the primary endpoint will be performed:*

- 1) We will compare the baseline AF burden and the baseline number of Apple watch-detected AF episodes between groups. The number of Apple watch-detected AF will be standardized by the number of days that a subject is under observation in the respective time period. Further we will compare reduction in AF burden from baseline at weeks 1, 2, 3 and 12 in both Group A and Group B to test the null hypothesis that there is no reduction of AF burden in the two groups and between the two groups. We will also compare the reduction in the number of Apple watch-detected AF episodes from the baseline in the period between week-3 and the end of study in both Group A and Group B to test the null hypothesis that there is no difference in detected AF episodes in the two groups and between the two groups. Linear mixed effect models will be used for the comparisons, with Group, Week and Group by Week interaction as fixed effects, and a random intercept per subject. Week will be coded first as a categorical variable, and appropriate contrasts will be set up for the temporal comparisons. If outcome variables appear to be linear in time, we may model Week as a continuous fixed effect.
- 2) We may also compute the difference-in-difference statistics for the treatment for the 4 time intervals of the treatment, baseline and t weeks 1, 2, 3 and 12.

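### The within-arm tests of no reduction in AF burden use a baseline selected for showing AF, so each arm is expected to show some fall without treatment; the randomised contrasts are unaffected

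*Combined protocol and SAP*

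**What the plan says.** Section 9.4.2, secondary analysis 1, compares the reduction in AF burden from baseline at weeks 1, 2, 3 and 12 "to test the null hypothesis that there is no reduction of AF burden in the two groups and between the two groups". The model is a linear mixed model with Group, Week and their interaction. Section 9.4.1 says that nominal two-tailed p values will be reported.

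The baseline is the qualifying recording. Section 9.4.2 states: "We will use Mobile Cardiac Telemetry to determine AF burden before surgery (eligibility visit". The schedule in section 1.3 marks mobile telemetry at Eligibility and not at Baseline, and the telemetry time points listed in section 8.1 do not include the Baseline visit. Section 5.1 requires AF burden "determined by a minimum of 7 days of continuous ePatch monitoring within 6 months before surgery", and section 1.2 says that patients with a usable ePatch result "do not have to undergo mobile cardiac telemetry during Eligibility visit".

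Entry depends on that recording showing AF. Section 5.2: "Patients without AF episodes during monitoring period will be excluded from the study and count as screen failure".

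Follow-up carries no such condition. Section 9.1: "Patients who do not experience AF during the first week will have a value of 0 as AF burden".

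**The concern.** Baseline burden cannot be zero, but follow-up burden can. Some patients qualify because the recording caught them in a worse-than-usual period, and nobody enters on an AF-free one. Regression to the mean then produces an average fall after entry in any arm, and a test of one arm against no change cannot separate that fall from a treatment effect.

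What is at stake is interpretation. Section 4.2 justifies the sham arm by the strong placebo effects of devices, and section 6.3 concedes that tingling or pain may make blinding difficult. A within-arm test sets that control aside. With about 10 evaluable patients per arm, a non-significant between-arm result beside a significant active-arm fall is a realistic outcome. As worded, the plan makes that within-arm fall a formal test result.

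**Working it through.** **1. The plan's own figure.** The effect size in section 9.2 is (76.3 − 5)/44.8 = 1.59. Simulated exact Wilcoxon power at two-sided 0.025 is 0.780 with 9 per arm and 0.829 with 10, so 10 evaluable patients are needed. With 70% retention, 10/0.70 = 14.3, rounded up to 15 per arm. The stated size is reproduced. It belongs to the between-arm test.

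**2. Direction and bound.** Let B0 and B1 be burden on the screening recording and in a later week, for all candidates. Suppose the disease is stable, so both have mean μ. A share q of candidates is AF-free at screening and excluded.

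- Mean baseline among those entered: μ/(1 − q).
- Mean follow-up among those entered: (μ − q·m)/(1 − q), where m is the later mean burden of those screened out.
- Relative fall = q·m/μ, the share of all later burden carried by the candidates who were screened out.

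This is positive whenever any of those candidates later has AF. If they carry no more burden than the average candidate (m ≤ μ), the fall is at most q: 10% when q = 10%, 30% when q = 30%. Simulation agrees with the identity: at correlation 0.5 and q = 30%, the fall is 8.8% and the screened-out share is 8.7%.

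**3. Size under assumptions.** Section 9.2 gives a median burden of 8.9% (IQR 3.4-25.2%). A lognormal fit has log-SD ln(25.2/3.4)/(2 × 0.6745) = 1.485; values are capped at 100%. Neither q nor the week-to-week correlation ρ is in the documents. Assumed ranges are q = 10-50% and ρ = 0.9 to 0.3. There is no treatment effect. A paired t test at an assumed two-sided 0.05 stands in for the mixed-model contrast, because the plan gives no level for these tests.

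| q | Mean burden, baseline → follow-up, ρ = 0.9 | Same, ρ = 0.3 | AF-free follow-up weeks | False reduction, n = 15 | False reduction, n = 10 |
|---|---|---|---|---|---|
| 10% | 22.23 → 22.16 (−0.3%) | 22.16 → 21.25 (−4.1%) | 2.5-7.8% | 2.1-3.2% | 1.5-2.4% |
| 30% | 27.79 → 27.38 (−1.5%) | 27.10 → 23.02 (−15.1%) | 6.4-21.3% | 2.9-6.6% | 2.3-4.6% |
| 50% | 36.19 → 34.83 (−3.8%) | 34.01 → 24.16 (−29.0%) | 10.4-34.8% | 4.4-16.0% | 3.5-13.1% |

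The nominal rate in the direction of reduction is 2.5%. With essentially no selection the same t test gives 1.3-2.3% at n = 15, so at q = 10% the inflation is slight. A signed-rank test runs somewhat higher (4.2-8.2% at q = 30%, n = 15). A second simulation on the burden scale gives false reduction of 1.4-3.2%, 2.1-6.0% and 2.8-12% for the three values of q. Taking the simulations together, the fall is about 0-4% at q = 10% and about 0-18% at q = 30%. The upper end also depends on how closely an AF-free recording goes with low underlying burden, which again has to be assumed.

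**4. Between-arm tests.** Selection precedes randomisation and is the same in both arms, so it cancels in the difference. Under the same selection and no effect, the between-arm test of change rejects in 1.9-2.8% of runs at 15 per arm and 1.3-2.2% at 10, against a nominal 2.5%.

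**The case against.** The strongest reply is that nothing in the plan makes a within-arm result evidence of efficacy. The primary test is between arms at 0.025, the synopsis frames the secondary objectives as differences between the randomised groups, and the model yields the randomised contrast alongside the within-arm ones. Entry asks only for some AF, so few candidates may be screened out and the bias may be small. All of this stands, and it limits the point to wording in a secondary analysis. It does not make the within-arm nulls valid tests of treatment.

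Section 1.2 also says that all patients have baseline rhythm monitoring, which could suggest a separate, unselected baseline. Neither the schedule nor the section 8.1 list provides such a telemetry recording at the Baseline visit, and section 9.4.2 names the eligibility visit.

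A reader might infer a larger, firmer inflation by simulating episode counts on a log scale. That gives a 10-20% fall in the geometric mean and false reduction in 4.7-6.5% of runs. The same simulated patients on the untransformed scale give only about 0.5-1%. The planned endpoint is percentage of time in AF, with no transformation stated, so the log-count figures do not measure the planned analysis.

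A reader might also extend the bias to the second secondary hypothesis in section 9.1, "that reduction of AF burden in treatment group does not depend on time versus that the reduction of AF burden is dependent on time". Comparing reductions between follow-up weeks cancels the shared baseline: (B − W1) − (B − W2) = W2 − W1. The simulated week 2 versus week 1 test rejects in about 2-3% per side, near nominal. Selection enters only if baseline is itself one of the time points. Recasting that hypothesis as a between-group comparison would largely repeat the first one in the same list.

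**Conclusion.** The point holds for the within-arm tests of AF-burden change from baseline, and only for those. The direction follows from three stated rules (eligibility recording as baseline, AF required on it, AF-free follow-up weeks scored 0), provided underlying AF is otherwise stable. The size is not bounded by anything in the documents. Under the assumed correlations it ranges from negligible to a relative fall of about 4% with 10% screened out or 18% with 30%, and a one-arm false-reduction rate of about 1-3% or 2-6%. Larger values need a screened-out share for which the documents give no support.

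A reader might conclude that untreated patients will visibly improve, or that the trial's efficacy result is biased. The documents support neither. The first depends on unknown quantities, and the second is wrong for the primary test, the Group-by-Week contrasts and the difference-in-difference. Apple Watch monitoring starts at the Baseline visit, so its baseline is not the recording used for selection and those counts fall outside this point.

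**What to change.** In section 9.4.2, secondary analysis 1, delete the within-group null tests of AF-burden change from baseline. Report each group's change at weeks 1, 2, 3 and 12 as an estimate with a confidence interval, labelled descriptive. State that efficacy conclusions rest only on the between-arm Group-by-Week contrasts of the same model. If the second secondary hypothesis in section 9.1 is still tested inside the treatment group, state that baseline is not one of its time points.

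This changes wording only: same model, same data, same 15 per arm. The small cost is that within-arm p values are no longer available.

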### 6.3 MEASURES TO MINIMIZE BIAS: RANDOMIZATION AND BLINDING

The patient will be consented to undergo surgery. After the device implantation, the patients will be randomized to experimental and control groups using Redcap. We will attempt to blind the patients, although the tingling or pain associated with the stimulation may make blinding difficult. All data analyses performed by the co-investigators and the rhythm analyses performed by the Mobile Cardiac Telemetry system technicians will be blinded. The experimental group will receive stimulation at 3.5 mA output, while the control group will receive no stimulation. Data will be obtained during this time to determine atrial arrhythmia frequencies in both groups. The device will then be removed at the end of the second week. After the third week, we will give the option to the control group to crossover to the experimental group. This group of patients will undergo a second procedure to receive stimulation at 3.5 mA and we will follow up for another 3 weeks and 3 months post second procedure.

We will tell the patients that they will be randomized into experimental group or control group during surgery. We will attempt to blind the patients, although the tingling or pain associated with the stimulation may make blinding difficult. We will explain to all patients they may or may not feel tingling and/or pain during the 2-week stimulation time but will not tell them which group they are assigned to. All data analyses performed by the co-investigators and the rhythm analyses performed by the 7-day non-invasive monitoring system technicians will be blinded. After 3 weeks post-procedure, we will unblind the control group to give them the option of crossing over to the experimental group to receive the treatment. If they agree, these group of patients will forego the 3-month follow-up visit and will proceed with a second procedure along with follow up visits post-second procedure. Data will be obtained during this time to determine AF burden in all groups.

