- Apple Watch Monitoring – An Apple Watch Series 7 and Apple iPhone 6s or later model will be given to the patient during Baseline visit and serve as a secondary monitoring system from Baseline to the completion of the 3 month visit 7-day Mobile Cardiac Telemetry. AF monitoring via Apple iPhone and Apple Watch will not be for safety monitoring. Previous studies have shown that the Apple Watch is able to detect episodes of Atrial Fibrillation in patients with high AF burden. The patients will wear the watch starting Baseline visit and will continue to wear it until the completion of the 3 Month Visit 7-day Mobile Cardiac Telemetry. The patient is to wear the watch as much as possible throughout the day and night. We will encourage subjects to use the Apple Watch's ECG App to record ECGs when the subject suspects they are in Atrial Fibrillation or receive a notification generated by the Apple Watch that a Low Heart Rate, High Heart Rate, or Irregular Rhythm was detected. This is a single-lead ECG that is able to provide information about heart rate, heart rhythm, and has ability to classify Atrial Fibrillation. ECG tracings can also be determined as inconclusive, meaning that the recording cannot be classified. iPhone 6s and later models are the only Apple devices that have the WatchApp, which is required for any data collected on the Watch to be transmitted to the HealthApp on the iPhone.

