We will compare the number of Apple watch-detected AF episodes between week-3 and the end of study between Group A and Group B to test the null hypothesis that there are no differences in detected AF episodes between the two groups. For each patient, we will record the number of days that the patient is under observation, and the number of days that AF episodes are detected. Assuming that each patient's data follows a binomial distribution and the probability of AF daily detection is the same within group. Since patients' data are independent from each other and the sum of independent binomials are still a binomial, we can compare the two groups as two binomials with potentially different rates of AF detections. Fisher's exact test will be performed for this comparison at a two-sided significance level of 0.05.

The overall scores of Quality of life (AFEQT-AF, EQ-5Q-5L) questionnaires will be compared at the following time points, baseline, 3 week and 3 month visits by the same linear mixed effect models as described for aSKNA. The same missing data treatment as stated above will be employed in the linear mixed model analyses of these two outcomes. Item and total scores may be transformed if deemed necessary to fulfil model assumptions.

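### The Apple Watch comparison of Group A with Group B after week 3 has no rule for sham patients who cross over, so as written it does not estimate ScNS versus sham

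*Combined protocol and SAP*

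**What the plan says.** Two secondary analyses use watch data after week 3.

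- Section 9.4.2 fits a linear mixed model to the "reduction in the number of Apple watch-detected AF episodes from the baseline in the period between week-3 and the end of study", within each group and between groups.
- Section 9.4.3 (Analysis of SKNA and QOL) states: "We will compare the number of Apple watch-detected AF episodes between week-3 and the end of study between Group A and Group B". It pools patient-days within each group, assumes that "the probability of AF daily detection is the same within group", and applies Fisher's exact test at two-sided 0.05.

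The crossover falls inside that window. Section 6.3 says that three weeks after the procedure "we will unblind the control group to give them the option of crossing over to the experimental group to receive the treatment", and section 6.1.2 gives that treatment as 3.5 mA ScNS. On timing, section 1.2 says: "Second procedure is to be done within two weeks of the Week 3 Visit for crossover patients". Under section 8.1 patients "will continue to wear it until the completion of the 3 Month Visit 7-day Mobile Cardiac Telemetry", with no exception for those who cross over.

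Membership of the modified intention-to-treat set (section 9.3) depends on stimulation or sham having been performed and on baseline and week-1 AF burden. Crossover plays no part. Section 9.4.3 uses this set for the secondary endpoints. Its only crossover-specific analysis describes AF burden up to week 6, with optional mixed models. It does not mention the watch and does not remove these patients from the Group A versus Group B tests.

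On visits, section 6.3 says: "If they agree, these group of patients will forego the 3-month follow-up visit and will proceed with a second procedure". The same section also says "we will follow up for another 3 weeks and 3 months post second procedure".

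**The concern.** The secondary objective in section 1.1 concerns the effect of ScNS between the randomized groups. After week 3 Group B is no longer purely a sham group. If accepters remain in it, their days during and after active stimulation enter the control arm, and the test contrasts ScNS with a mixture of sham and ScNS. Stimulation lasts only two weeks, but section 2.3.2 proposes that the benefit may persist afterwards, so on the trial's own hypothesis the later days are affected too. If stimulation works, the assumption of one daily detection probability within Group B also fails.

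At stake is what the trial can say about effects beyond week 3. A lasting benefit would look smaller than it is, or a result would be described as ScNS versus sham when it answers another question. Without a written rule, the handling could also be chosen after Group B has been unblinded.

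**Working it through.** **No plan figure to reproduce.** The documents give no sample size, power or expected uptake for the watch comparison. The 15 per arm in section 9.2 concerns week 1, before any crossover.

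**Inputs from the documents.** The window opens at day 21. The second procedure normally falls within 14 days of the week-3 visit, so by about day 35. The watch is worn to the end of the 7-day telemetry at 3 months.

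**Assumptions.** Three months is day 91, or day 98 with the 7-day telemetry. The second procedure is on day p = 22 to 35. Uptake is 50% unless stated.

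**Step 1: share of an accepter's window during or after active ScNS** = (end - p)/(end - 21).
- End day 91: p = 22 gives 69/70 = 0.99; p = 28 gives 63/70 = 0.90; p = 35 gives 56/70 = 0.80.
- End day 98: 76/77 = 0.99; 70/77 = 0.91; 63/77 = 0.82.

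**Step 2: share of all Group B watch-days affected.**

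| Follow-up of accepters | Calculation at 50% uptake | Share |
|---|---|---|
| To day 91 | 0.5 x 0.80 to 0.5 x 0.986 | 40-49% |
| To day 98 | 0.5 x 0.818 to 0.5 x 0.987 | 41-49% |
| To 91 days after second procedure (0-14 days' wait; others 70 days) | 91/(105 + 70) to 91/(91 + 70) | 52-57% |
| To 98 days after second procedure (p = 22-35; others 77 days) | 98/(112 + 77) to 98/(99 + 77) | 52-56% |
| Stop at repeated 3-week visit (21 affected days; others 77 days) | 21/(35 + 77) to 21/(22 + 77) | 19-21% |

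With follow-up to day 91, other uptakes give 20-25% (25% uptake) and 64-79% (80% uptake).

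**Step 3: dilution.** Let f be the affected share. If ScNS acts at once, lasts, and works equally in both groups, the Group B rate is (1 - f) x sham rate + f x ScNS rate, and the expected difference shrinks by f. With assumed daily detection of 0.50 (sham) and 0.25 (ScNS):
- f = 0.40: Group B = 0.400, difference 0.150 instead of 0.25.
- f = 0.493: Group B = 0.377, difference 0.127.

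**Step 4: does this example produce a false null?** I applied the planned pooled-day Fisher test with 700 days per arm (10 patients x 70 days) and 0.25 in Group A.
- Group B 0.400: p = 3e-9. Group B 0.377: p = 4e-7.
- 80% uptake, earliest procedure, Group B 0.303: p = 0.031.
- The same rates with 490 days per arm: p = 0.07.

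The estimate is diluted. Significance is lost only at high uptake with fewer days. These p-values treat days as independent, as the plan does, and so flatter the evidence; that is a separate weakness.

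**Step 5: visit outcomes at week 12/3 months.** Accepters miss the original 3-month visit, so observed Group B values come from unblinded patients who did not cross over. Under the planned mixed model (compound symmetry, assumed within-patient correlation 0.5-0.8, Group A complete, half of Group B measured at the last visit), the standard error of the change contrast rises by a factor of about 1.14 with five time points, or 1.15-1.17 with the three quality-of-life time points. Section 9.4.3 assumes missing at random for SKNA and quality of life. Its last-value-carried-forward sensitivity analysis would set an accepter's week-3 value against Group A at 3 months. For AF burden, section 9.4.2 offers only a general baseline-covariate adjustment for differential drop-out and does not mention crossover.

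**The case against.** No passage says that crossover days count as sham days. A reader might infer this as a stated rule; it is an inference from an unrestricted comparison and a set that ignores crossover. The protocol describes the move as one into the experimental group, so reassignment is conceivable, though less natural for a modified intention-to-treat analysis. What stands is that the handling is not specified.

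An as-randomized comparison preserves randomization and, under the assumptions above, errs toward the null. That is a legitimate choice if declared, but the text does not declare it.

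A reader might also infer that a real effect would be missed. Step 4 does not show that.

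It would also be too strong to call the end of study undefined. Section 1.2 ties it to the final week of outpatient monitoring, and the participant duration of up to 5 months in section 1.1 fits a 3-month visit after the second procedure. But the footnote to the schedule in section 1.3 limits the 3-month visit to Group A and to controls who do not cross over, whereas sections 1.1, 1.2 and 6.3 describe follow-up after the second procedure that includes it. The end of an accepter's watch window depends on which passage is followed.

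Finally, the amendment history calls the later data secondary and exploratory. That limits the weight of the point, but sections 9.4.2 and 9.4.3 still state between-group hypotheses on those data, one with a significance level.

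**Conclusion.** The point holds for secondary analyses only and should be fixed. The watch comparison after week 3 has no crossover rule. On the natural reading it estimates immediate versus optional delayed ScNS, and its single within-group detection probability fails if stimulation works. The size rests on assumed uptake, procedure day and length of follow-up: at 50% uptake, 40-57% of Group B days are affected with follow-up to about 3 months, and 19-21% if accepters stop at the repeated 3-week visit. Proportional shrinkage of the difference further requires an effect that is immediate, lasting and equal in both groups. The week-12/3-month visit contrasts are a lesser issue of lost precision, possible selection and unblinded ratings.

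**What to change.** In sections 9.4.2 and 9.4.3:

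- Limit formal ScNS-versus-sham inference to data through week 3.
- Keep the week-3-to-end watch comparison and the week-12/3-month contrasts as exploratory, and name the as-randomized version as immediate versus optional delayed ScNS.
- Add a sensitivity analysis that ends each Group B patient's contribution at the second procedure and standardizes by uncrossed days observed. State that this introduces selection, because crossover is unblinded and self-chosen.
- Do not carry an accepter's week-3 value forward to 3 months.
- Reconcile the section 1.3 footnote with sections 1.1, 1.2 and 6.3 on whether accepters have a 3-month visit after the second procedure, so that the end of their watch window is fixed.

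The cost is a text amendment with IRB approval (Statement of Compliance) and the loss of a formal long-term between-arm test. With 10 Group B patients x 70 days and 5 crossing over, the sensitivity analysis keeps 350 + 5 x 1 = 355 to 350 + 5 x 14 = 420 of 700 days (51-60%), mostly from patients who did not cross over.
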